Study start and end time	
The recruitment period for the randomized comparison part is estimated to be 8 months. The recruitment period for the expansion part is estimated to be 4 months.
 
Estimated start time: December 2012
 
Enrollment completion time for the expansion part: January 24, 2014
 
End time: October 24, 2014

Study objectives	
Primary objective:
 
To randomly compare the safety and tolerability of two different administration methods of Fruquintinib (4mg qd daily vs. 5mg qd 3-week on/1-week off) in treatment of patients with advanced colorectal cancer who have failed with standard care (evaluated according to CTCAE4.0), as to further determine the recommended dose for phase II/III clinical studies.
 
To further observe and evaluate the safety, tolerability and efficacy (progression-free survival) of Fruquintinib 5mg qd 3-week on/1-week off in treatment of patients with advanced colorectal cancer who have failed with standard care during the expansion

	part.
	
Secondary objective:
 
 To compare the objective response rate (ORR), disease control rate (DCR), duration of response (according to RECIST 1.1 criteria), progression-free survival (PFS) and overall survival (OS) between two groups To compare the pharmacokinetic profile of two different administration methods of Fruquintinib monotherapy in treatment of advanced colorectal cancer Expansion part- to further observe the DCR, ORR and OS of Fruquintinib in treatment of advanced colorectal cancer

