Subjects Terminating Study	the Criteria on completion of the trial: 1. Progression of disease 2. Death 3. Inability to recover to \leq NCI CTC AE Grade 1 or baseline within 14 days after dose interruption 4. NCI CTC AE Grade 4 (nephrotic syndrome) in routine urinalysis or 24-hour urine protein quantification; CTC AE Grade 4 abnormal hepatic function and hemorrhage Criteria on premature discontinuation: 1. The subject becomes pregnant. 2. The investigator judges the termination of the study in the subject's best interest; 3. The subject or his/her legal representative requestes withdrawal from the study; 4. The subject is lost to follow-up 5. Serious violation from the study protocol
End of the whole trial	The whole trial ends 9 months after the end of enrollment for the expansion part.
Statistical analysis:	SAS 9.2 software is used for analysis, where the pharmacokinetic parameters are calculated using WinNonlin software. The detailed statistical method will be provided in the statistical analysis plan. In the randomized comparison part, statistical analysis and comprehensive evaluation will be performed for the primary parameters including safety and tolerability (overall incidence of adverse events, incidence of G3/4 adverse events, incidence of serious adverse events, incidence of adverse events leading to dose interruption and permanent discontinuation of the drug) and secondary parameters including the efficacy, as to determine the recommended dose for phase II/III trials. In the expansion part, the safety, tolerability and efficacy of Fruquintinib 5mg 3-week on/1-week off are further evaluated in patients with advanced colorectal cancer. The primary endpoints (safety, tolerability and progression-free survival at Week 16) are analyzed three months after the inclusion of the last subject in the expansion part. The overall survival is analyzed 9 months after the inclusion of the last subject in the expansion part.
Efficacy	To perform statistical description of objective response rate (proportion of subjects with complete response or partial response as the optimal overall response, according to RECIST1.1 criteria), DCR, DOR, PFS and OS.

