4.6 End of Trial

End of the whole trial is defined as 9 months after enrollment of the last patient.

There are a few situations for end of trial for each subject as below:

- 1 Death
- 2 The subject or his/her legal representative requests to withdraw from the study and refuses to be followed up.
- 3 The subject is lost to to follow-up
- 4 End of the whole trial

The database will be locked after the end of the whole trial. For subjects who have not reached PFS event, the sponsor will continue to provide the product if they are willing to continue the administration after investigator's evaluation, and they will be followed up in accordance with the original schedule for treatment period (including safety evaluation, tumor assessment, drug counting) until progression of disease, death or loss of follow-up, or voluntary withdrawal from the trial. The sponsor is responsible for paying the cost for safety evaluation and tumor assessment but not for collection of data. If any SAE occurs during treatment, one SAE form needs to be filled in by investigators and reported to the sponsor. Survival of all the subjects will not be followed up after the end of the whole trial.

5 Treatment

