6.2 Clinical Assessment

6.2.1 Effectiveness

6.2.1.1 Effectiveness endpoint

All the effectiveness endpoints in the randomized comparison study are secondary endpoints.

Secondary endpoints:

Objective response rate (ORR) determined in accordance with RECIST1.1

Disease control rate (CR+PR+SD), where SD \geq 8 weeks

Duration of response

Progression-free survival (PFS)

Overall survival (OS)

Primary effectiveness endpoint in the expansion part is the progression-free survival at Week 16

The secondary endpoints are DCR, ORR and OS

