6.2.1.2 Assessment of effectiveness

The tumor is evaluated in accordance with RECIST1.1 criteria, and the detailed evaluation criteria are provided in Appendix 2. The radiological evaluation of tumors could use CT or MRI as decided by investigators, however, the apparatus and technical parameters should keep consistent throughout the study; contrast agent should be used in case of no contraindications. If the tumor evaluation has been performed 14-21 days before the first dose, and the same method and apparatus are used in the same hospital, this evaluation could be used as the baseline tumor evaluation. The baseline tumor evaluation should include neck, chest, abdomen, pelvis and any other sites that are suspected to have tumor lesions. Bone scan should be used for follow-up of the disease in patients with bone metastasis.

Record of target lesions: number, site and description of lesions, the maximum diameter measured for each lesion (except lymph node) and the minimum diameter measured for lymph node, sum of diameters including all the target lesions;

Subjects will receive the first tumor evaluation after 2 cycles of treatment, and one evaluation every two cycles subsequently, until progression of disease. If complete response or partial response occurs, it needs to be confirmed after 4 weeks. If the patient interrupts the dose for adverse drug reaction or other reasons, the tumor evaluation will be performed once every 8 weeks as originally scheduled. If the patient discontinues the study drug within 56 days, the tumor evaluation should be performed as early as possible after discontinuation of the drug.

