8.1 Primary and secondary research variables

Primary variables:

Overall incidence of adverse events

Incidence of Grade 3/4 adverse events

Incidence of serious adverse events

Incidence of adverse events leading to permanent discontinuation

Incidence of adverse events leading to interruption/reduced dose

16-week progression-free survival rate

Secondary variable:

Effectiveness:

"Event occurrence date" variable: Calculated since the day when the informed consent is signed. If no event is observed, there is no date of end, and a so called cutoff observation has to be considered for analysis. The cutoff date is: The last date, such as for "last tumor measurement", "last medication registration", or "last visit".

Secondary efficacy variables include objective response rate, disease control rate, duration of response, progression-free survival, and overall survival.

Objective response rate (ORR): defined as the incidence of confirmed complete response (CR) or partial response (PR), the target lesions and non-target lesions are evaluated with validated radiological method and judged in accordance with RECIST criteria 1.1.

Progression-free survival (PFS): defined as the time from the signature of informed consent form to the first recording of progression of disease (PD) or date of death, whichever comes first. If no PD is observed, the censoring date should be the date of the last tumor measurement.

Overall survival (OS): defined as the time from the signature of informed consent form to date of death for any reason. If no death is observed, the last follow-up date is regarded as the censoring date.

Disease control rate (DCR): defined as the incidence of confirmed complete response (CR), partial response (PR) and stable disease (SD), the target lesions and non-target lesions are

evaluated with validated radiological method and judged in accordance with RECIST criteria 1.1.

Duration of response: defined as the time from the first recording of CR or PR to the first finding of PD for patients who have achieved response. For those with no record of PD after CR or PR, the censoring date is the date of the last tumor measurement.

Safety and Tolerability:

Safety and tolerability of the treatment are evaluated by incidence and severity of adverse events, laboratory tests, vital signs, ECG, LVEF, and ECOG performance status.

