8.2.2 Statistical Methods

Efficacy Analysis:

Randomized comparison part-secondary efficacy endpoint analysis:

The inter-group difference of objective response rate is compared by CMH Chi-square test.

Secondary efficacy endpoint analysis: Descriptive statistical analysis.

Progression-free survival is analyzed by Kaplan-Meier method;

Overall survival is analyzed by Kaplan-Meier method;

The inter-group difference of disease control rate is compared by CMH Chi-square test;

The duration of response is analyzed by Kaplan-Meier method; the median time to response and its 95% confidence interval are listed for the two groups.

Expansion part- primary efficacy endpoint analysis:

The 16-week progression-free survival rate is calculated in patients with advanced colorectal cancer who have failed with standard care and are receiving drug administration of 5 mg qd 3-week on/1-week off in the study. Secondary endpoints are analyzed by descriptive statistical analysis.

At the end of the trial, the survival (including median survival and 9-month survival rate) in patients with advanced colorectal cancer who have failed with standard care and are receiving drug administration of 5 mg qd 3-week on/1-week off is analyzed.

Safety analysis:

Safety analysis population: The safety analysis population includes the patients signing the informed consent who receive at least one dose of the treatment.

All safety parameters are summarized, and are tabulated by the safety population.

The frequency table (overall and by intensity) of adverse events is listed by system organ class. In the table of the overall incidence of adverse event, subjects with the same adverse event more than once is only counted once in the frequency table.

Shift table and frequency table are used simultaneously for summary of laboratory data according to sampling timepoint.

All the AEs and abnormal laboratory variables are evaluated according to CTCAE v4.0 grading system.

ECOG performance status will be summarized by descriptive statistics. Vital signs, ECG, and echocardiography will be described by tabulation.

During the randomized comparison part, inter-group differences are compared by CMH Chi-square test, based on the primary safety endpoints.

The overall incidence of adverse events, incidence of G3/4 adverse events, and severe adverse events are compared between the two groups;

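### The analysis of PFS at Week 16 in the expansion part is set at three months after the last inclusion, about three weeks before the last subject's Week-16 scan is due

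*Protocol*

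**What the plan says.** The statistical analysis row of the protocol synopsis fixes the timing for the expansion part: "The primary endpoints (safety, tolerability and progression-free survival at Week 16) are analyzed three months after the inclusion of the last subject". It places the overall survival analysis at 9 months after the same event.

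The endpoint is not in doubt. Section 6.2.1.1 states: "Primary effectiveness endpoint in the expansion part is the progression-free survival at Week 16". Section 8.2.2 adds: "The 16-week progression-free survival rate is calculated in patients with advanced colorectal cancer". No estimator is named there; Kaplan-Meier is named for PFS only under the randomized part.

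Three other provisions bear on when the endpoint can be known:

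- **Clock.** Section 8.1 has PFS "defined as the time from the signature of informed consent form to the first recording of progression of disease (PD) or date of death".
- **Censoring.** Section 8.1 also says: "If no PD is observed, the censoring date should be the date of the last tumor measurement".
- **Scans.** Section 6.2.1.2 says: "Subjects will receive the first tumor evaluation after 2 cycles of treatment, and one evaluation every two cycles subsequently, until progression of disease". A cycle is 28 days, so scans fall at about Day 56 and Day 112 of treatment. A response is confirmed 4 weeks after it is first seen.

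On accrual, the synopsis says: "The recruitment period for the expansion part is estimated to be 4 months". It dates the end of expansion enrollment 24 January 2014 and the end of the trial 24 October 2014. On the data, Section 4.6 says: "The database will be locked after the end of the whole trial".

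**The concern.** Three months is shorter than sixteen weeks. Under the stated rule, the primary efficacy endpoint of the expansion part is analyzed before the last subjects included can have had the scan that decides it.

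The expansion part is a single arm of about 20 patients, so each undetermined outcome carries weight, and there is no control arm in which the same shortfall would occur. The interim analysis of the randomized part (Section 8.2.4) is tied to completed treatment cycles. The expansion analysis has no such condition, and nothing elsewhere in the protocol gives a later cut-off for this endpoint or requires every subject to have reached Week 16.

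**Working it through.** **Inputs from the protocol.** Last expansion inclusion 24 January 2014, end of trial 24 October 2014, expansion accrual 4 months (all synopsis); 20 expansion subjects (Section 3.2); scans every 8 weeks of treatment (Section 6.2.1.2); preliminary median PFS of 3.7 months in the 3-week on/1-week off group (Section 3.1.2).

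**Assumptions.** Uniform accrual; first dose on the day of inclusion; exponential PFS, with no difference between the consent and treatment clocks in the survival figures; month length 30.44 days.

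**1. The plan's own figure.** 24 January 2014 plus 9 calendar months is 24 October 2014, the stated end date. The protocol therefore counts calendar months from the last inclusion.

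**2. The three-month cut-off.** 24 January plus 3 months is 24 April 2014: 90 days, or 90/7 = 12.9 weeks. Week 16 is 16 × 7 = 112 days, which is 16 May 2014 for the last subject. Shortfall: 112 − 90 = 22 days. With a generic three months of 91 days it is 21 days.

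**3. Counting from consent.** If consent precedes inclusion by L days, the last subject has 90 + L days on the PFS clock at the cut-off.

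| L (days) | Days from consent | Short of 112 by | Expected subjects short, 20 × shortfall/122 |
|---|---|---|---|
| 0 | 90 | 22 | 3.6 |
| 7 | 97 | 15 | 2.5 |
| 14 | 104 | 8 | 1.3 |
| 21 | 111 | 1 | 0.2 |

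The protocol does not fix L. The flowchart's screening column starts at Day −14, and Section 6.2.1.2 accepts a baseline scan from 14 to 21 days before first dose, so 21 days is taken as the upper end.

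**4. The scan.** An event-free subject is censored at the last tumor measurement, not at the cut-off. For the last subject included, that is Day 56 of treatment, or Day 56 + 28 = 84 for a responder with a confirmatory scan. Adding a 21-day consent lead gives 77 and 105 days, both below 112. The second scheduled scan depends on treatment, so the consent lead does not bring it forward.

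**5. Subjects without the Week-16 scan.** Four months back from 24 January 2014 is 24 September 2013, an accrual period of 122 days.

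- Protocol dates: 20 × 22/122 = 3.6 (18%).
- Generic months: 20 × 21/(4 × 30.44) = 3.4 (17%).

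**6. Of these, still undetermined.** With a median of 3.7 × 30.44 = 112.6 days:

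- S(56) = 2^(−56/112.6) = 0.708
- S(112) = 2^(−112/112.6) = 0.502

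Undetermined: 3.4 × 0.708 = 2.4 to 3.6 × 0.708 = 2.5. The remainder have already progressed or died.

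**7. Effect on a simple proportion.**

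- Undetermined subjects counted as progression-free: 3.4/20 × (0.708 − 0.502) = +3.5 points; with 3.6, +3.7 points.
- Undetermined subjects dropped: with 3.6, (16.4 × 0.502)/(20 − 2.55) = 0.472, or −3.0 points; with 3.4, (16.6 × 0.502)/(20 − 2.41) = 0.474, or −2.8 points.

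For scale, the standard error of a proportion near 0.5 with 20 subjects is √(0.25/20) = 0.112, about 11 points.

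**The case against.** The case for leaving the sentence alone has four parts.

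- **Kaplan-Meier could use the censored subjects.** The SAP, which is not shown, may specify it. This is fair, and it would avoid both counting rules in the working. But follow-up would still be thin at the one time point that is the endpoint.
- **The data are not lost.** The lock follows the 9-month end of trial, so a complete Week-16 rate can be produced later. This stands and limits the harm. It also means that little is gained by the early cut-off.
- **Any shift is small against sampling error.** About 3 points compares with a standard error of about 11, and the sample size section sets no threshold that the shift could overturn. This stands.
- **The consent origin shortens the gap.** This also stands on the PFS clock, but a lead of up to 21 days does not close the gap and does nothing to the scan date.

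A reader might also infer more than the protocol supports:

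- That 29-31% of subjects are affected. Those figures (5.7 and 6.2 of 20) need a lag of up to 14 days from inclusion to first dose and, for the higher one, a 3-day scan window. The protocol gives no such lag. Section 6.1 places screening before inclusion, and the flowchart shows no window at Day 112.
- That no late-included subject has an outcome at the cut-off. Those who have progressed or died by then are resolved.
- That the primary result rests on censored subjects. On these assumptions, outcomes are determinable for about 17 to 18 of 20.
- That the rate is biased upward by 3 to 4 points. That needs a simple proportion with unassessed subjects counted as progression-free, a rule the protocol does not state.

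**Conclusion.** The timing rule is wrong as written: 90 days cannot deliver a 112-day endpoint for the last subjects included. The date arithmetic uses only the protocol's own dates, and the conclusion holds for every consent lead tried, up to 21 days.

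The size is modest. About 3 to 4 of 20 subjects lack the Week-16 scan at the cut-off, given uniform accrual and dosing at inclusion. About 2 to 3 of those have undetermined status, given also exponential PFS with the preliminary 3.7-month median. The consequence is a shift of roughly 3 points either way under a simple proportion, or reduced precision under Kaplan-Meier. This is a correctable scheduling error in a descriptive single-arm part, and it does not invalidate the endpoint.

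**What to change.** In the statistical analysis row of the synopsis, detach PFS at Week 16 from the three-month rule. Set its data cut-off at the point when the last expansion subject has had the Week-16 tumor assessment, or has earlier progressed, died or withdrawn. The safety and tolerability analysis can keep its present timing or move with it.

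By the protocol's dates, four calendar months after the last inclusion is 24 May 2014. That is 120 days (17.1 weeks), which covers Day 112 and an assumed 3-day window (Day 115, 19 May). A longer interval is needed only if first dose lags inclusion.

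The cost is one sentence and a later readout: 22 days to the last subject's Week-16 date, or 30 days to the four-month mark, so about 3 to 4 weeks. Both fall well before the 9-month end of trial and the lock that follows it.

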HFS	Hand-foot syndrome
HUVEC	Human umbilical vein endothelia cell
IARC	International Agency for Research on Cancer
IC50	Half inhibitory concentration
ICH	International Conference on Harmonisation

Abbreviations and Special Term	Explanation
IDMC	Independent Data monitoring committee
INR	International normalized ratio
ITT	Intent-to-treat
LDH	Lactic Dehydrogenase
LOAEL	Lowest observed adverse effect level
LVEF	Left ventricular ejection fraction
MedDRA	Medical Dictionary for Regulatory Activities
mg	Milligram(s)
ml	Millilitre(s)
MRI	Magnetic resonance imaging MRP
MTD	Maximum tolerated dose
NCCN	National Comprehensive Cancer Network
NCI	National Cancer Institute
NCI-CTC	National Cancer Institute Common Toxicity Criteria
NCI-CTCAE	National Cancer Institute Common Terminology Criteria for Adverse Events
NE	Non-Evaluable
NOAEL	No observed adverse effect level
NSCLC	Non-small-cell lung carcinoma
ORR	Objective response rate
OS	Overall survival
PD	Progressive disease or pharmacodynamics
PDGFR	Platelet derived growth factor receptor
PFS	Progression-free Survival
p.o.	per os
PR	Partial response
PS	Performance status
PSA	Prostate-specific antigen
PT	Prothrombin time
QD	Qd
RECIST	Response Evaluation Criteria in Solid Tumors
SAE	Serious adverse event
SD	Stable disease/standard deviation
TG	Triglyceride
TKi	Tyrosine kinase inhibitor
TP	Total protein
TT	Thrombin time
TTP	Time to Progression
TSH	thyroid stimulating hormone

Abbreviations and Special Term	Explanation
VEGF	Vascular endothelial growth factor
VEGFR	Vascular endothelial growth factor receptor
WHO	World Health Organization

1. Background

1.1 Colorectal cancer

Colorectal cancer is one of the most common malignancies, and ranks No.3 in the incidence among all the malignancies worldwide, regardless of male or female. In the western developed countries, colorectal cancer is the 2nd common malignancy in incidence, and took the No. 3 place in both the number of newly developing cases and mortality in US in 2003. As shown in the data provided by the International Agency for Research on Cancer (IARC), the incidence of colorectal cancer also increases rapidly in Asian, in particular in economically developed regions, and is approaching that in western countries. Colorectal cancer has been the second tumor in terms of incidence and mortality in our country since 2010, its incidence has reached 56/100,000 in the developed regions along the coast and showed a trend of onset in younger patients. In Shanghai, the incidence of colorectal cancer is increasing by 4.2% per year on average, it has taken the 2nd place among common malignancies and accounted for 13.08% of all the malignancies. Chemotherapy is the main therapy for advanced colorectal cancer. The chemotherapeutic agents commonly used in clinical practice include 5FU/LV, capecitabine, irinotecan and oxaliplatin, and their combination regimen are mostly used for chemotherapy. In recent years, the monoclonal antibody bevacizumab targeting vascular endothelial growth factor (VEGF), the monoclonal antibody cetuximab and panitumumab targeting EGFR have been combined with chemotherapy respectively as the first-line therapy for patients with advanced colorectal cancer, and have significantly improved the therapeutic outcome in these patients^[1-2]. The 2nd-line chemotherapy is the main therapy for patients with colorectal cancer who have failed with the 1st-line therapy, mechanisms of the 2nd-line therapeutic agents vary, selection of treatment is mainly dependent on the type of tumor, duration of chemotherapy as well as the side and toxic effects of the drug. The efficacy and safety of some drugs still need to be further evaluated^[2-3]. The selective kinase inhibitor of VEGFR from Bayer healthcare, regorafenib was approved by FDA for treatment of advanced colorectal cancer after failure of the 2nd-line chemotherapy in 2012, its main endpoint, the median survival was prolonged by 1.4 month as compared with placebo (6.4m vs 5.0m), and the hazard ratio was 0.773 (p=0.0051)^[4].

Angiogenesis is the most critical process in the occurrence and progression of malignant tumors. The study found the angiogenesis in tumor area provided nutrients for the tumor and took away metabolites, and tumor cell could transfer to other sites via the new blood vessels. Thus, effective inhibition of the angiogenesis in tumor area could inhibit the growth of tumor cells, and reduce the occurrence of metastasis. Currently, anti-tumor angiogenesis has become the most promising novel strategy for treatment of tumors. Development of tumor angiogenesis is associated with multiple vessel-related factors, rapidly growing tumor cells secrete various vascular growth factors under anoxic condition and stimulate tumor angiogenesis. One of the important growth factors is vascular endothelial cell growth factor (VEGF). VEGFR is currently found to be one of the main inducing factors related with tumor angiogenesis, thus VEGF/VEGFR signaling pathway is considered as one of the

most promising targets in molecular targeted therapy of tumors^[5].

In recent years, the successful advent of the monoclonal antibody bevacizumab for treatment of advanced colorectal cancer and breast cancer, Sunitinib (Sutent) for treatment of renal carcinoma, sorafenib (Nexavar) for treatment of hepatic carcinoma and renal carcinoma, and other small molecular targeted antitumor agents in succession not only exhibited an astonishing market outlook, but also brought the traditional therapy of tumors towards individualized comprehensive therapy, allowing numerous patients to benefit from control of tumor and prolonged survival. The giant success of VEGF highly selective monoclonal antibody, bevacizumab in clinical practice fully demonstrated the effectiveness of this target and its importance in R & D of new drugs. Currently, the available new drug Sunitinib and sorafenib in the market are classified as inhibitors for multi-target small molecular kinase including vascular endothelial cell growth factor receptor (VEGFR). These drugs inhibit tumor angiogenesis kinase and cancer cell growth signaling kinase at the same time. Excessive inhibition of kinase, however would cause great toxic and side effects. Research and development of the selective 2nd generation of VEGFR have become the hot spot globally.

Fruquintinib, researched and developed by Hutchison Medi Pharma (Shanghai) Co., Ltd., is a potent small molecular compound using VEGFR kinase family as the target and closely related with angiogenesis, with complete proprietary intellectual property rights. Fruquintinib mainly acts on the transmembrane receptor family (VEGFR1, 2 and 3) on vascular endothelial cells (vascular endothelial growth factor receptor, VEGFR) and has a very high selectivity for kinase. The 50% inhibitory concentration (IC₅₀) was measured to be 35nM, 33nM and 0.5nM for VEGFR1, 2 and 3, respectively. However, Fruquintinib had no inhibitory activity on a variety of kinases related with cell cycle or proliferation, including cyclin-dependent kinase (CDK1, 2, 5), epidermal growth factor receptor (EGFR) and mesenchymal-epithelial transition factor (c-Met) (IC₅₀>3μM). Fruquintinib had no obvious inhibitory activity on platelet-derived growth factor receptor (PDGFRβ) kinase as well (IC₅₀>1 μM), thus demonstrating a good selectivity at molecular level.

